5.1.1.3 Hepatic Effects

Background

Liver toxicity has been reported with other class drugs that target $\alpha 4$ integrins (natalizumab) and $\alpha 4\beta 7$ integrins (vedolizumab). Therefore, this potential risk is being monitored in all etrolizumab studies. In nonclinical chronic toxicology studies, no abnormalities indicating liver toxicity with etrolizumab were observed. The risk in humans is currently unknown.

Education, Monitoring, and Management

Patients should receive guidance on reporting liver problems if they occur. Liver function tests should continue to be monitored according to the schedule of assessments and as clinically indicated. Significant hepatic events should be evaluated promptly and managed accordingly.

5.1.1.4 Local Injection-Site Reactions

Background

A local injection-site reaction is any local reaction occurring at the site of injection following study drug administration. In completed Phase I/II trials, injection-site reactions were reported at a rate of $\leq 10\%$, all of which were of mild intensity.

Monitoring

In the clinic setting, patients should be monitored for signs of injection-site reactions in the period immediately following injections. Patients should be given guidance on reporting injection-site reactions when administering drug at home or after the patient leaves the clinic.

5.1.1.5 Malignancies

Background

There has been no evidence for increased incidence of malignancy in completed Phase I/II trials and nonclinical studies to date. Nonetheless, given the elevated risk of

malignancy in this patient population a priori, the study includes selection criteria and additional information to minimize any hypothetical risk.

Patient Selection

Patients who developed a malignancy (with the exception of local and resected basal or squamous cell carcinoma of the skin) during Study GA29144, including AIS, HSIL, or CIN of Grade > 1 or colonic dysplasia, are to be excluded from this study.

Monitoring and Management

Investigators should remain vigilant for signs or symptoms of malignancy in scheduled study assessments, including those of potential lymphoma.

Any signs or symptoms that could be suggestive of malignancy should be promptly and aggressively evaluated and reported to the Sponsor. Incident hematologic abnormalities (e.g., new or worsening neutropenia, anemia, thrombocytopenia, macrocytosis, or atypical cells in the WBC differential) should be carefully evaluated.

Patients who develop a malignancy (with the exception of local and resected basal or squamous cell carcinoma of the skin) or who develop AIS, HSIL, or CIN of Grade > 1 on cervical Pap smear or who develop colonic dysplasia during the study should be withdrawn from study drug and must not receive additional doses of study drug.

5.1.1.6 Immunogenicity Background

As with administration of any exogenous protein, a potential exists for the development of ATAs. Such antibodies can be neutralizing with potential for reducing therapeutic effect of the drug and/or sensitizing, with potential for allergic reactions. On the basis of the clinical experience to date, approximately 5% of patients develop ATAs to etrolizumab; however, this has not been correlated with any efficacy or safety sequelae.

Monitoring

To assess for the potential development of immunogenicity, antibody samples will be obtained at baseline, at regular intervals during treatment, and during the Safety Follow-Up Period (see [Appendix 1](#) and [Appendix 2](#)), and stored appropriately for further evaluation as needed.

5.1.1.7 Decreased Effectiveness of Immunizations Background

The effect of etrolizumab upon the efficacy of vaccinations is unknown.

Patient Selection and Risk Mitigation

Patients who received a live attenuated vaccine during Study GA29144 or within 4 weeks prior to enrollment in the OLE are excluded from the study. Patients should not receive live attenuated vaccines during the study and for at least 5 half-lives (approximately 12 weeks) after final study drug administration.

5.1.2 Risks Associated with Worsening of Crohn's Disease

The worsening of CD may result in the use of rescue medications. In severe cases, worsening of CD may lead to hospitalization or require surgery.

At any time during the study, patients who have worsening of their CD will be permitted to receive additional therapy with corticosteroids (IV, oral, or topical). Addition of or increases in doses of immunosuppressants (i.e., AZA, 6-MP, or MTX) will also be allowed if clinically indicated by the Principal Investigator.

Rescue therapy with anti-TNF agents (including TNF inhibitor biosimilars), cyclosporine, tacrolimus, sirolimus, MMF, natalizumab, vedolizumab, anti-adhesion agents, rituximab, other lymphocyte depleting agents (except AZA and 6-MP, or equivalent), or other biological or investigational therapeutics will not be allowed in conjunction with etrolizumab because of the level of immunosuppression anticipated with the use of these agents. Patients who receive any of these prohibited rescue medications are not to receive further treatment with etrolizumab, are to complete the 12-week safety follow-up, and should then enter into Part 2 (SM) of the study.

See Section 4.4.2 and Appendix 1 for the schedule of assessments to be performed in the event of worsening of CD, which may lead to an unscheduled visit.

5.1.3 Data Monitoring Committee

An independent Data Monitoring Committee (iDMC) will monitor safety and study conduct for Study GA29144 on an ongoing basis until the study is unblinded to the Sponsor. Safety data from Study GA29145 will also be available for review by the iDMC on an ongoing basis to inform their assessment of the overall safety of etrolizumab in CD.

Members of the iDMC will be external to the Sponsor and will follow a charter that outlines the iDMC roles and responsibilities. The iDMC will meet approximately every 6 months (frequency adjustable as required) to review data prepared by an independent data coordinating center. The iDMC may recommend stopping the study early for safety reasons.

Because of the open-label design of the OLE-SM study, the Sponsor will retain the primary responsibility for monitoring its safety and study conduct.

5.2 SAFETY PLAN (PART 2, SM)

PML Monitoring Part 2 (SM)

Following the 12-week safety follow-up period in Study GA29144 or in Part 1 (OLE) of the OLE-SM study, all patients are to continue to be monitored for PML for an additional 92 weeks (extended PML monitoring) in Part 2 (SM) of this study, providing a total of 2 years PML follow-up after the last dose of study drug. No etrolizumab will be administered during this time.

PML monitoring during this period will consist of the PML assessment interview conducted by telephone at intervals of approximately 6 months (see [Appendix 3](#)). Any signs or symptoms suggestive of PML or cases of suspected PML (see [Appendix 8](#)) should be documented and handled and expeditiously reported to the Sponsor as adverse events of special interest or serious adverse events, as appropriate, within 24 hours, as described in Section [5.1.1.1.1](#) and [Appendix 9](#) (Algorithm for the Evaluation of Progressive Multifocal Leukoencephalopathy). Study site personnel and patient participants will be educated regarding the signs and symptoms of PML and suspected cases of PML will be managed as in Section [5.1.1.1.1](#). Patients are to be instructed to contact the investigator immediately if they experience signs and/or symptoms suspected to be PML between the 6-month telephone intervals.

5.3 SAFETY PARAMETERS AND DEFINITIONS

Safety Assessments during Part 1 (OLE)

Safety assessments in Part 1 (OLE) will consist of monitoring and recording adverse events, including serious adverse events and adverse events of special interest; measurement of protocol-specified safety laboratory assessments; measurement of protocol-specified vital signs; and other protocol-specified tests that are deemed critical to the safety evaluation of the study.

Certain types of events require immediate reporting to the Sponsor, as outlined in Section [5.5](#).

Safety Assessments during Part 2 (SM)

Safety assessment in Part 2 (SM) will consist of only PML monitoring with use of the PML Subjective Checklist conducted by telephone at intervals of approximately 6 months (see [Appendix 3](#)) during which any signs or symptoms suggestive of PML (see [Appendix 8](#)) will be documented and handled as described in Section [5.1.1.1](#) and [Appendix 9](#) (Algorithm for the Evaluation of Progressive Multifocal Leukoencephalopathy).

5.3.1 Adverse Events

According to the ICH guideline for Good Clinical Practice, an adverse event is any untoward medical occurrence in a clinical investigation patient administered a pharmaceutical product, regardless of causal attribution. An adverse event can therefore be any of the following:

- Any unfavorable and unintended sign (including an abnormal laboratory finding), symptom, or disease temporally associated with the use of a medicinal product, whether or not considered related to the medicinal product
- Any new disease or exacerbation of an existing disease (a worsening in the character, frequency, or severity of a known condition), except as described in Sections [5.4.6.9](#) and [5.4.6.10](#)

- Recurrence of an intermittent medical condition (e.g., headache) not present at baseline
- Any deterioration in a laboratory value or other clinical test (e.g., ECG, X-ray) that is associated with symptoms or leads to a change in study treatment or concomitant treatment or discontinuation from study drug
- Adverse events that are related to a protocol-mandated intervention, including those that occur prior to assignment of study treatment (e.g., screening invasive procedures such as biopsies)

5.3.2 Serious Adverse Events (Immediately Reportable to the Sponsor)

A serious adverse event is any adverse event that meets any of the following criteria:

- Fatal (i.e., the adverse event actually causes or leads to death)
- Life threatening (i.e., the adverse event, in the view of the investigator, places the patient at immediate risk of death)

This does not include any adverse event that had it occurred in a more severe form or was allowed to continue might have caused death.

- Requires or prolongs inpatient hospitalization (see Section [5.4.6.11](#))
- Results in persistent or significant disability/incapacity (i.e., the adverse event results in substantial disruption of the patient's ability to conduct normal life functions)
- Congenital anomaly/birth defect in a neonate/infant born to a mother exposed to study drug
- Significant medical event in the investigator's judgment (e.g., may jeopardize the patient or may require medical/surgical intervention to prevent one of the outcomes listed above)

The terms "severe" and "serious" are not synonymous. Severity refers to the intensity of an adverse event (rated as mild, moderate, or severe, or according to National Cancer Institute Common Terminology Criteria for Adverse Events (NCI CTCAE) criteria; see Section [5.4.4](#)); the event itself may be of relatively minor medical significance (such as severe headache without any further findings).

Severity and seriousness need to be independently assessed for each adverse event recorded on the eCRF.

Serious adverse events are required to be reported by the investigator to the Sponsor immediately (i.e., no more than 24 hours after learning of the event; see Section [5.5.2](#) for reporting instructions).

5.3.3 Adverse Events of Special Interest (Immediately Reportable to the Sponsor)

Adverse events of special interest are required to be reported by the investigator to the Sponsor immediately (i.e., no more than 24 hours after learning of the event; see Section 5.5.2 for reporting instructions). Adverse events of special interest for this study include the following:

- Cases of potential drug-induced liver injury that include an elevated ALT or AST in combination with either an elevated bilirubin or clinical jaundice, as defined by Hy's law (Section 5.4.6.7)
- Suspected transmission of an infectious agent by etrolizumab, as defined below:

Any organism, virus, or infectious particle (e.g., prion protein transmitting transmissible spongiform encephalopathy), pathogenic or non-pathogenic, is considered an infectious agent. A transmission of an infectious agent may be suspected from clinical symptoms or laboratory findings that indicate an infection in a patient exposed to a medicinal product. This term applies only when a contamination of the study drug is suspected.
- Adverse events of special interest specific to etrolizumab:

Systemic hypersensitivity reactions and anaphylactic and anaphylactoid reactions (see Section 5.1.1.2 and Clinical Criteria for Diagnosing Anaphylaxis in Appendix 10)

Neurological signs, symptoms, and adverse events that may suggest possible PML, on the basis of a positive finding on the PML Subjective Checklist that is accompanied by a positive finding on the PML Objective Checklist, or if there is strong clinical suspicion for PML (see Appendix 9 Algorithm for the Evaluation of Progressive Multifocal Leukoencephalopathy and Section 5.1.1.1)

5.4 METHODS AND TIMING FOR CAPTURING AND ASSESSING SAFETY PARAMETERS

5.4.1 Adverse Event Reporting Period for Part 1 (OLE)

After informed consent has been obtained, all adverse events, regardless of relationship to study drug, will be reported until the patient completes Part 1 (OLE).

During Part 1 (OLE), the investigator is responsible for ensuring that all adverse events (see Section 5.3.1 for definition) are recorded on the Adverse Event eCRF and reported to the Sponsor in accordance with instructions provided in this section and in Sections 5.5, 5.6, and 5.7. The investigator is also responsible for reporting medical device complaints (see Section 5.5.4).

For each adverse event recorded on the Adverse Event eCRF, the investigator will make an assessment of seriousness (see Section 5.3.2 for seriousness criteria), severity (see Section 5.4.4), and causality (see Section 5.4.5).

Investigators will seek information on adverse events at each patient contact. All adverse events, whether reported by the patient or noted by study personnel, will be recorded in the patient's medical record and on the Adverse Event eCRF. Past resolved adverse events will be recorded in the medical history according to their medical relevance. Adverse events reported ongoing at the end of Study GA29144 will be stated unresolved in that study and also reopened in Study GA29145. The adverse event will be reported with the start date and adverse event term identical to those in Study GA29144. Intensity should be evaluated by the investigator at the start of Part 1 (OLE) with the intensity entered into the initial intensity field for the event in the eCRF for Study GA29145. Additionally, the most extreme NCI CTCAE grade for the event that occurs during Study GA29145 should also be recorded in the eCRF for Study GA29145.

All adverse events following patient informed consent to the study, regardless of relationship to study drug, will be reported until the patient completes Part 1 (OLE).

Some patients may not enroll into Part 2 (SM), although all patients will be strongly encouraged to enter. For those patients who do not enroll into Part 2 (SM) (i.e., withdraw consent from the study), the Sponsor should be notified if post-study the investigators becomes aware of any serious adverse events that are believed to be related to prior study drug treatment (see Sections 5.7.1). In addition, the Sponsor should be notified if the investigator becomes aware of any post-study events of confirmed or suspected PML, regardless of relationship to study drug, for up to 2 years after the patient's last dose of study drug.

5.4.2 Adverse Event Reporting Period for Part 2 (SM)

Part 2 (SM) of the OLE-SM study is focused on extended follow-up for PML. During Part 2 (SM), the investigator will use the PML assessment interview to monitor for signs and symptoms of PML. All adverse events suggestive of PML, regardless of relationship to study drug, should be expeditiously reported to the Sponsor as adverse events of special interest or serious adverse events, as appropriate, within 24 hours.

The eCRF will be available during Part 2 (SM) to only report any adverse events of special interest or serious adverse events that may suggest possible PML or confirmed PML. Refer to the eCRF help instructions for more details. If the eCRF system is not available, then the process for submitting non-PML events (see below) should be followed.

The investigator is not required to actively monitor patients for other non-PML adverse events during Part 2 (SM); however, the investigator should notify the Sponsor if they become aware of any other non-PML serious adverse events that are believed to be related to prior study drug treatment. The investigator should report such events directly to Roche or its designee either by faxing or by scanning and e-mailing the Serious Adverse Event/Adverse Event of Special Interest Reporting Form using the fax number or e-mail address provided to investigators

5.4.3 Eliciting Adverse Event Information in Part 1 (OLE)

A consistent methodology of non-directive questioning should be adopted for eliciting adverse event information at all patient evaluation timepoints. Examples of non-directive questions include the following:

“How have you felt since your last clinic visit?”

“Have you had any new or changed health problems since you were last here?”

5.4.4 Assessment of Severity of Adverse Events

The adverse event severity grading scale for the NCI CTCAE (v4.0) will be used for assessing adverse event severity. [Table 2](#) will be used for assessing severity for adverse events that are not specifically listed in the NCI CTCAE.

Table 2 Adverse Event Severity Grading Scale for Events Not Specifically Listed in NCI CTCAE

Grade	Severity
1	Mild; asymptomatic or mild symptoms; clinical or diagnostic observations only; or intervention not indicated
2	Moderate; minimal, local, or non-invasive intervention indicated; or limiting age-appropriate instrumental activities of daily living ^a
3	Severe or medically significant, but not immediately life-threatening; hospitalization or prolongation of hospitalization indicated; disabling; or limiting self-care activities of daily living ^{b,c}
4	Life-threatening consequences or urgent intervention indicated ^d
5	Death related to adverse event ^d

NCI CTCAE = National Cancer Institute Common Terminology Criteria for Adverse Events.

Note: Based on the most recent version of NCI CTCAE (v4.0), which can be found at: http://ctep.cancer.gov/protocolDevelopment/electronic_applications/ctc.htm

- ^a Instrumental activities of daily living refer to preparing meals, shopping for groceries or clothes, using the telephone, managing money, etc.
- ^b Examples of self-care activities of daily living include bathing, dressing and undressing, feeding one's self, using the toilet, and taking medications, as performed by patients who are not bedridden.
- ^c If an event is assessed as a "significant medical event," it must be reported as a serious adverse event (see Section 5.5.2 for reporting instructions), per the definition of serious adverse event in Section 5.3.2.
- ^d Grade 4 and 5 events must be reported as serious adverse events (see Section 5.5.2 or reporting instructions), per the definition of serious adverse event in Section 5.3.2.

5.4.5 Assessment of Causality of Adverse Events

Investigators should use their knowledge of the patient, the circumstances surrounding the event, and an evaluation of any potential alternative causes to determine whether an adverse event is considered to be related to the study drug, indicating "yes" or "no" accordingly (see [Table 3](#)). The following guidance should be taken into consideration:

- Temporal relationship of event onset to the initiation of study drug
- Course of the event, considering especially the effects of dose reduction, discontinuation of study drug, or reintroduction of study drug (where applicable)
- Known association of the event with the study drug or with similar treatments
- Known association of the event with the disease under study
- Presence of risk factors in the patient or use of concomitant medications known to increase the occurrence of the event
- Presence of non-treatment-related factors that are known to be associated with the occurrence of the event

Table 3 Causal Attribution Guidance

Is the adverse event suspected to be caused by the study drug on the basis of facts, evidence, science-based rationales, and clinical judgment?	
YES	There is a plausible temporal relationship between the onset of the adverse event and administration of the study drug, and the adverse event cannot be readily explained by the patient's clinical state, intercurrent illness, or concomitant therapies; and/or the adverse event follows a known pattern of response to the study drug; and/or the adverse event abates or resolves upon discontinuation of the study drug or dose reduction and, if applicable, reappears upon re-challenge.
NO	Adverse events will be considered related, unless they fulfill the criteria as specified below. Evidence exists that the adverse event has an etiology other than the study drug (e.g., preexisting medical condition, underlying disease, intercurrent illness, or concomitant medication); and/or the adverse event has no plausible temporal relationship to administration of the study drug (e.g., cancer diagnosed two days after first dose of study drug).

5.4.6 Procedures for Recording Adverse Events

Investigators should use correct medical terminology/concepts when recording adverse events on the Adverse Event eCRF. Avoid colloquialisms and abbreviations.

Only one adverse event term should be recorded in the event field on the Adverse Event eCRF.

PART 1 (OLE)

All ongoing adverse events from Study GA29144 should be entered on the Adverse Event eCRF.

All new adverse events that occur during Part 1 (OLE) should be entered on the Adverse Event eCRF.

PART 2 (SM)

Record on the Adverse Event eCRF ONLY event-related neurological abnormalities (signs/symptoms that may suggest possible PML) identified on both the PML Subjective AND PML Objective Checklist or if there is a strong clinical suspicion for PML as an adverse event of special interest or serious adverse event, as appropriate. Each abnormality should be reported as a separate adverse event of special interest. Do NOT report events as "Suspected PML" or "Rule out PML." If there is a confirmed diagnosis of PML, report this diagnosis as a serious adverse event.

In Part 2 of the study, all events that may suggest possible PML should be entered on the Adverse Event eCRF. All other non-PML serious adverse events that the investigator becomes aware of and believes to be related to prior study drug treatment should be reported to the Sponsor via faxing/e-mailing the paper serious adverse event reporting form.

5.4.6.1 Injection-Site Reactions

Local cutaneous adverse events that occur at or around the injection site during or within 24 hours after study drug injection should be captured as individual signs (e.g., erythema, induration/swelling at injection site) and symptoms (e.g., pain, pruritus at injection site) rather than a diagnosis of allergic reaction or injection site reaction.

5.4.6.2 Diagnosis versus Signs and Symptoms

For adverse events other than injection-site reactions (see Section 5.3.1), a diagnosis (if known) should be recorded on the Adverse Event eCRF rather than individual signs and symptoms (e.g., record only liver failure or hepatitis rather than jaundice, asterixis, and elevated transaminases). However, if a constellation of signs and/or symptoms cannot be medically characterized as a single diagnosis or syndrome at the time of reporting, each individual event should be recorded on the Adverse Event eCRF. If a diagnosis is subsequently established, all previously reported adverse events based on signs and symptoms should be nullified and replaced by one adverse event report based on the single diagnosis, with a starting date that corresponds to the starting date of the first symptom of the eventual diagnosis.

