5.4.6.4 Persistent or Recurrent Adverse Events

A persistent adverse event is one that extends continuously, without resolution, between patient evaluation timepoints. Such events should only be recorded once on the Adverse Event eCRF. The initial severity (intensity or grade) of the event will be recorded at the time the event is first reported in this study. For adverse events ongoing from the parent study, the current intensity of the event at this study start will be recorded as the initial intensity for the event in this study. If a persistent adverse event becomes more severe, the most extreme severity should also be recorded on the Adverse Event eCRF. If the event becomes serious, it should be reported to the Sponsor immediately (i.e., no more than 24 hours after learning that the event became serious; see Section 5.5.2 for reporting instructions). The Adverse Event eCRF should be updated by changing the event from "non-serious" to "serious," providing the date that the event became serious, and completing all data fields related to serious adverse events.

A recurrent adverse event is one that resolves between patient evaluation timepoints and subsequently recurs. Each recurrence of an adverse event should be recorded as a separate event on the Adverse Event eCRF.

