1.3.2 Safety Outcome Measures

The safety outcome measures for GA29145 Part 1 (OLE) of this study are as follows:

- Incidence and severity of adverse events
- Incidence of serious adverse events
- Incidence, rate per subject-year, and severity of infection-related adverse events
- Incidence of serious infection-related adverse events
- Incidence and severity of injection-site reactions
- Incidence of adverse events leading to etrolizumab discontinuation
- Incidence of laboratory abnormalities
- Incidence and rate per subject-year of malignancies
- Incidence and severity of hypersensitivity reactions

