Summary tables will be generated for AEs, serious adverse events (SAEs), deaths, AEs leading to discontinuation of study drug, and AESIs. A listing will be generated for AEs, deaths, selected AESIs/specific AEs, and COVID-19 AEs. Pregnancies will be reported as narratives in the study CSR.

Summary tables of AEs will summarize the incidence of treatment-emergent AEs only. Treatment-emergent events are defined as any new AE reported on or after the first dose of OLE study drug or any worsening of an existing condition. Note that worsening of existing conditions include AEs ongoing from the parent study, GA29144. Otherwise, only AEs reported on or after the first dose of OLE study drug are included. If the onset date of the AE is prior to the day of first dose, the AE will be considered treatment emergent only if the most extreme intensity is greater than the initial intensity (i.e., the intensity for a given AE increases and its end date is on or after the date of the first dose). For all summary tables, the AEs will be sorted by SOC (in decreasing order of overall incidence) and then by preferred term (PT) (in decreasing order of overall incidence).

For OLE etrolizumab treatment, the incidence count for each AE PT will be defined as the number of patients reporting at least one treatment-emergent occurrence of the event (multiple occurrences of the same AE in 1 patient will be counted only once). The proportion of patients with an AE will be calculated as the incidence count divided by the total number of patients in the population. Each table will also present the total number of AEs reported where multiple occurrences of the same AE in an individual are counted separately.

Rate tables will be generated for selected AEs of interest. The rate per 100 patient years and 95% CIs will be summarized by treatment group and will be calculated by:

$$AE \text{ Rate (per 100 patient years)} = \frac{\text{Total number of AEs (in OLE only)}}{\text{Total number of patient years at risk (in OLE only)}} \times 100$$

where the total patient-years at risk is the sum over all patients of the time intervals (in years) from the first dose of study treatment in Part 1 (OLE) until the patient completes/withdraws from the study (including the 12-week safety follow-up, if applicable). Only treatment emergent AEs with an onset date after the first dose of open label Etolizumab in GA29145 will be included within these outputs.

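### A diagnosis made during the OLE that replaces a symptom event carried over from GA29144 can take a pre-OLE onset date and so drop out of the malignancy and infection rates per patient-year

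*Protocol*

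**What the plan says.** Four rules meet here.

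- **Replacement and back-dating.** Under Protocol 5.4.6.2, a diagnosis that emerges later cancels the symptom records entered so far and takes their place as one record, "with a starting date that corresponds to the starting date of the first symptom of the eventual diagnosis". The rule sets no floor at the first OLE dose.
- **Carried-over events.** For events ongoing at the end of GA29144, Protocol 5.4.1 says: "The adverse event will be reported with the start date and adverse event term identical to those in Study GA29144".
- **Rate tables.** SAP 4.2.2 says: "Only treatment emergent AEs with an onset date after the first dose of open label Etolizumab in GA29145 will be included within these outputs". It makes no exception for worsening, seriousness or a new diagnosis. The denominator is the sum of all patients' time from the first OLE dose to completion or withdrawal, including safety follow-up.
- **Incidence tables.** SAP 4.2.2 is less strict here. For an onset before the first dose, "the AE will be considered treatment emergent only if the most extreme intensity is greater than the initial intensity".

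SAP 1.3.2 lists "Incidence and rate per subject-year of malignancies" as a safety outcome, and likewise the rate per subject-year of infection-related events. Both are also named among the other safety objectives in SAP 1.1 and Protocol 2.2. Neither document has a rule for a diagnosis first made on OLE treatment whose first recorded symptom predates the first OLE dose.

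**The concern.** Each rule is ordinary taken alone. Together they can remove from a named safety rate an event that was found while the patient was on OLE treatment. The loss runs in one direction: a case leaves the numerator and nothing leaves the denominator. It is also selective, because it falls on slow-onset disease that announces itself first as a recorded symptom. Protocol 5.1.1.5 itself asks investigators to follow up new or worsening blood abnormalities such as anaemia as possible signs of malignancy.

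The study is descriptive, with no comparison arm and no test, so the tabulated rate is itself the result. Malignancies are likely to be few, and one case more or less then changes the figure a reader takes away.

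**Working it through.** **Tracing one case (illustrative).** A patient has anaemia recorded as an adverse event in GA29144, unresolved at OLE entry. A malignancy is diagnosed at OLE Week 30 and judged to explain the anaemia.

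1. Protocol 5.4.1: the anaemia is entered in GA29145 with its GA29144 start date, which is before the first OLE dose.
2. Protocol 5.4.6.2: the anaemia record is nullified. The malignancy record takes that start date.
3. SAP 4.2.2, rate table: onset is not after the first OLE dose, so the event is excluded at any grade.
4. SAP 4.2.2, incidence table: the event is included only if the most extreme intensity exceeds the initial one. Protocol 5.4.6.4 says: "The initial severity (intensity or grade) of the event will be recorded at the time the event is first reported in this study". If the replacement record is graded afresh at diagnosis, no rise need appear. If it inherits the symptom's grade at OLE start, a rise probably would. The documents do not say which applies.
5. SAP 4.2.2, listings: adverse events, deaths and selected specific events are listed, so the case should still be visible there.

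**An unreconciled pair.** Step 2 assumes that Protocol 5.4.6.2 governs carried-over symptoms. Protocol 5.4.1 requires the GA29144 term to be kept unchanged. If that prevails, the symptom record stays, the malignancy is entered as a new event with an OLE onset, and the rate counts it. The same clinical course can therefore be counted or not according to which section the site follows.

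**Size.** The plan states no event count, person-time or expected rate, so there is no figure to reproduce. The SAP formula is rate = 100 × E / T, with E events and T patient-years. If k of the E events are back-dated before the first OLE dose, the tabulated rate is 100 × (E − k) / T. The ratio to the full rate is (E − k) / E = 1 − k/E, so the proportional fall equals the back-dated share and does not depend on T.

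All inputs below are assumptions. Intervals are exact Poisson 95%; the SAP does not name its method.

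With E = 5 and T = 1,000:

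- k = 0: 100 × 5/1,000 = 0.50 (0.16–1.17)
- k = 1: 100 × 4/1,000 = 0.40 (0.11–1.02), 20% lower
- k = 2: 100 × 3/1,000 = 0.30 (0.06–0.88), 40% lower

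With E = 10 malignancies and T = 1,150 × 1, 2 or 3 years (1,150 being the stated maximum enrolment), the rates per 100 patient-years are:

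| T | k = 0 | k = 1 | k = 2 | k = 3 |
|---|---|---|---|---|
| 1,150 | 0.870 (0.417–1.599) | 0.783 (0.358–1.486) | 0.696 (0.300–1.371) | 0.609 (0.245–1.254) |
| 2,300 | 0.435 (0.208–0.800) | 0.391 (0.179–0.743) | 0.348 (0.150–0.685) | 0.304 (0.122–0.627) |
| 3,450 | 0.290 (0.139–0.533) | 0.261 (0.119–0.495) | 0.232 (0.100–0.457) | 0.203 (0.082–0.418) |

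The k = 0 column is also the result if no case is affected, which is quite possible.

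**The case against.** The strongest reply is that this is how treatment-emergence is meant to work. SAP Section 3 focuses on events arising after the first OLE dose. Disease already symptomatic before that dose is conventionally left out, and counting by diagnosis date would bring in disease that began before OLE exposure, including in former placebo patients before any etrolizumab. That stands as a reason to keep the onset-based rate. It is not a reason to show that rate alone when the onset date is an administrative back-dating of a diagnosis made on treatment.

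The trigger is also narrow. The symptom must already be a recorded adverse event, be unresolved at OLE entry and be judged part of the same disease; Protocol 5.4.6.3 keeps events separate when the link is unclear. A cancer found incidentally, with no earlier symptom record, is not back-dated by this rule. Protocol 4.1.2 also keeps out of the OLE most patients with a malignancy recognised in GA29144 and those with an unresolved serious infection. All of this stands and limits the number of cases.

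Three stronger inferences are tempting but not supported:

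- **Gut infections are lost on a large scale.** Protocol 5.4.6.10 makes anticipated Crohn's symptoms adverse events only when they worsen unexpectedly or change in nature, so often there is no symptom record to replace.
- **The diagnosis is counted in neither study.** Protocol 5.4.1 says only that the event is left unresolved in GA29144. How that study updates its records cannot be known from these documents.
- **The events vanish from reporting.** The exclusion is absolute only for the rate tables.

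**Conclusion.** The gap is real but limited. For a symptom event carried over from GA29144 and later replaced by a diagnosis under Protocol 5.4.6.2, the SAP rate rule removes a diagnosis newly made in the OLE from the rate per patient-year, whatever its grade. This rests on reading 5.4.6.2 as applying to carried-over symptoms, which the documents neither confirm nor exclude. Malignancies are the main concern, with serious infections a lesser one.

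The number of cases is unknown and may be zero or very few. The 20% and 40% falls above follow wholly from assumed counts, and the intervals overlap heavily; they are not estimates of bias in this study. What can be said firmly is that the tabulated rate falls by exactly the affected share and can never rise through this route. That justifies a modest change to the SAP, not replacement of its onset convention.

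**What to change.** In SAP 4.2.2:

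1. Keep the onset-based rate as planned.
2. For malignancies and serious infections, add a second rate line that also counts diagnoses first established, or first reported in GA29145, on or after the first OLE dose even if the recorded start date is earlier. Use dates already held: the date the diagnosis was first reported in GA29145, or the date the event became serious. The latter is recorded under Protocol 5.4.6.4 only for events that change from non-serious to serious, so it will not serve every case.
3. Exclude from the second line any diagnosis already made before the first OLE dose and merely carried over.
4. List the cases that differ between the two lines beside the rate.
5. State how Protocol 5.4.1 (same term and start date) and 5.4.6.2 (term replaced) are reconciled for carried-over symptoms, and how initial intensity is set for a replacement record.

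The cost is a little extra programming. The second line may include disease that began before OLE exposure, which showing both lines makes plain. No new case report form field is proposed: the sponsor terminated the OLE on 15 February 2022 with last dosing on 15 May 2022 (SAP 1.4 and 4.1.1), so a diagnosis date would have to be collected retrospectively.
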